Whilst blinding is an important consideration for any clinical study, the objectives of this study are not to investigate product efficacy, but to develop a methodology. To fulfil the objectives of this study it is not possible to adequately maintain blinding and therefore this study will be conducted open label.

 GlaxoSmithKline	Document Name	208397 Clinical Protocol 2.docx		
	Type	Version	Document Identifier	Effective Date
	eldo_controlled	2.0; Most Recent; Effective; CURRENT	090032d580db1b91	24-Oct-2017 08:49:05
	Reason For Issue	Auto Issue		

Sodium-calcium mixed partial salt of poly(methylvinylether/maleic acid) and carboxymethylcellulose

208397

Final Clinical Protocol, 20 Oct 2017

The Kapur-Olshan index is a composite score based upon stability and retention ratings for the maxillary and mandibular dentures ([Kapur, 1967](#); [Olshan, 1992](#)). In this study, subject recruitment will be targeted to achieve approximately equal numbers of subjects in the low and high Kapur-Olshan groups. The low Kapur-Olshan group is defined as a composite Kapur-Olshan score of 6-14 (clinically fair and good dentures) and the high Kapur-Olshan score as 15-18 (clinically very good dentures), values derived from consideration of previous study data ([205915, 2016](#)). The purpose of this analysis is to explore the optimum inclusion criteria for future studies. Subjects presenting with a very low Kapur-Olshan score at Screening (<6), defined as "Clinically Poor" ([Olshan, 1992](#)), will be excluded from this study.

Denture adhesive achieves its function by physical means and once completely removed from the denture does not have any residual effects. Therefore, the 2-30 day period between each test day is considered adequate rest for the oral soft tissues from the stresses of mastication encountered in this study.

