2 STUDY OBJECTIVES AND ENDPOINTS

Table 2-1 Study Objectives and Endpoints

Objectives	Endpoints
Primary	
To evaluate the mass of peanut particles that migrate under the dentures during a food occlusion methodology when denture adhesive is applied per conventional pattern.	Mass of peanuts under combined maxillary and mandibular dentures.
Exploratory	
To evaluate the mass of peanut particles that migrate under the dentures during a food occlusion methodology when denture adhesive is applied per continuous strips pattern and when no adhesive is used.	Mass of peanuts under combined maxillary and mandibular dentures.
To evaluate the mass of peanut particles that migrate under the maxillary and mandibular dentures during a food occlusion methodology when denture adhesive is applied per conventional pattern, continuous strips pattern and when no adhesive is used.	Mass of peanuts under maxillary dentures. Mass of peanuts under mandibular dentures.
To evaluate subject responses to 2 questions during a food occlusion methodology when denture adhesive is applied per conventional pattern, continuous strips pattern and when no adhesive is used.	Subject completed questionnaire.
To explore the performance of a marketed denture adhesive when applied per conventional pattern to no adhesive use for subjects in the low and high Kapur-Olshan subgroups.	Mass of peanuts under combined maxillary and mandibular dentures in each subgroup (low and high Kapur-Olshan scores).
To explore the relationship between the number of subject-reported denture dislodgements when denture adhesive is applied per conventional pattern, continuous strips pattern and when no adhesive is used.	The number of subject reported denture dislodgements during chewing.
Safety	
To assess the tolerability of marketed denture adhesive (Super Poligrip Free).	Treatment emergent adverse events.

This study is a method development study and therefore there is no formal success criterion.

Document Name	208397 Clinical Protocol 2.docx	Document Identifier	Effective Date
Type	Version		
eldo_controlled	2.0; Most Recent; Effective; CURRENT	090032d580db1b91	24-Oct-2017 08:49:05

Sodium-calcium mixed partial salt of poly(methylvinylether/maleic acid) and carboxymethylcellulose

208397

Final Clinical Protocol, 20 Oct 2017

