10 STATISTICAL CONSIDERATIONS AND DATA ANALYSES

10.1 Sample Size Determination

Since this is an exploratory methodology development study, no formal sample size calculation was conducted. CCI

Therefore, approximately 48 (maximum 50) healthy subjects with both maxillary and mandibular full dentures will be enrolled in this study. Subject recruitment will be controlled to ensure 50±10% of the subjects will be in each of the low and high Kapur-Olshan groups [the low Kapur-Olshan group is defined as a composite Kapur-Olshan score of 6-14 (clinically fair and good dentures) and the high Kapur-Olshan score as 15-18 (clinically very good dentures)].

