10.2.8 Additional Analyses

For future development work, adjusted means of masses of peanuts recovered from mandibular, maxillary and combined dentures, along with 95% confidence interval will also be reported by treatment group. These will be derived from a mixed model with period and treatment as fixed effects and subject as a random effect. Treatment differences and 95% confidence intervals of treatment differences will be reported.

Using the same model as above, a subgroup analysis will be also conducted in low and high Kapur-Olshan groups of subjects. Adjusted means of combined masses of peanuts recovered from mandibular and maxillary denture, along with 95% confidence interval will be reported by treatment groups for each sub-group.

These results will be reported in the statistical appendix as part of the CSR.

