1.2 Study Objectives

The study objectives are as follows:

Objectives	Endpoints
Primary Objective	Primary Endpoint

To evaluate the mass of peanut particles that migrate under the dentures during a food occlusion methodology when denture adhesive is applied per continuous strips pattern and when no adhesive is used.	
Mass of peanuts under combined maxillary and mandibular dentures.
Exploratory Objectives	Exploratory Endpoints

To evaluate the mass of peanut particles that migrate under the dentures during a food occlusion methodology when denture adhesive is applied per continuous strips pattern and when no adhesive is used.	
Mass of peanuts under combined maxillary and mandibular dentures.

To evaluate the mass of peanut particles that migrate under the maxillary and mandibular dentures during a food occlusion methodology when denture adhesive is applied per conventional pattern, continuous strips pattern and when no adhesive is used.	
Mass of peanuts under maxillary dentures.Mass of peanuts under mandibular dentures.

To evaluate subject responses to questions during a food occlusion	
Subject completed questionnaire.

Objectives	Endpoints
methodology when denture adhesive is applied per conventional pattern, continuous strips pattern and when no adhesive is used.	

 To explore the performance of a marketed denture adhesive when applied per conventional pattern to no adhesive use for subjects in the low and high Kapur-Olshan subgroups. To explore the relationship between the numbers of subject-reported denture dislodgements when denture adhesive is applied per conventional pattern, continuous strips pattern and when no adhesive is used. 	
 Mass of peanuts under combined maxillary and mandibular dentures in each subgroup (low and high Kapur-Olshan scores). The number of subject reported denture dislodgements during chewing.
Safety	

 To assess the tolerability of marketed denture adhesive (Super Poligrip Free). 	
 Treatment emergent adverse events.

This study is a method development study and therefore there is no formal success criterion.

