3.2 Subgroups/Stratifications

The subgroups defined in this study are as follows:

Low Kapur-Olshan group: Defined as a composite Kapur-Olshan score of 6-14 (clinically fair and good dentures) at screening.

High Kapur-Olshan group: Defined as a composite Kapur-Olshan score of 15-18 (clinically very good dentures) at screening.

Exploratory analysis will be performed on the above defined subgroups.

Stratification factors are not defined in this study.

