4.6 Additional Analysis

Adjusted means for mass of peanuts recovered from mandibular, maxillary (Table 16.1.9.2.1) and combined (Table 16.1.9.1.1) dentures, along with 95% confidence interval (CI) will also be reported by treatment group. These will be derived from a mixed model with period and treatment as fixed effects and subject as a random effect. The pair-wise comparisons will be performed and corresponding treatment differences, SE and 95% CI will be presented for all patients in ITT population. No p-value will be reported.

Using the same model as above, a subgroup analysis will be also conducted in low and high Kapur-Olshan groups of subjects. Adjusted means of combined masses of peanuts recovered from mandibular and maxillary denture, along with 95% CI will be presented by treatment groups for each sub-group (Table 16.1.9.3.1) for all patients in ITT population.

These results will be reported in the statistical appendix as part of CSR.

The assumptions underlying the mixed model will be examined using appropriate statistical method and if necessary, a suitable transformation of data or alternative non-parametric method based on ranks will be applied to obtain the inferential statistics. Hodges-Lehmann estimates of median of differences and Hodges-Lehmann 95% confidence intervals will be calculated.

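### The Kapur-Olshan subgroup output meets its objective as worded, but one low-minus-high row with a 95% CI would bear directly on the stated purpose of exploring inclusion criteria.

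*SAP*

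**What the plan says.** The exploratory objective in Protocol section 2 (Table 2-1) concerns adhesive "applied per conventional pattern to no adhesive use for subjects in the low and high Kapur-Olshan subgroups". SAP 1.2 repeats it, and the endpoint in SAP 4.5.1 is combined peanut mass in each subgroup. All of this is worded within group.

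Protocol 1.2.1 gives the reason for the grouping: "The purpose of this analysis is to explore the optimum inclusion criteria for future studies". Recruitment is managed for it. Protocol 10.1 states: "Subject recruitment will be controlled to ensure 50±10% of the subjects will be in each of the low and high Kapur-Olshan groups".

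On analysis, Protocol 10.2.8 and SAP 4.6 agree. SAP 4.6 reads: "Using the same model as above, a subgroup analysis will be also conducted in low and high Kapur-Olshan groups of subjects". That model has period and treatment as fixed effects and subject as random, with no group term. SAP 3.2 adds only: "Exploratory analysis will be performed on the above defined subgroups".

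The shell of Table 16.1.9.3.1 prints, separately for Low (6-14) and High (15-18), three adjusted means and three pairwise treatment differences with SE and 95% CI. It has no row comparing the groups. The SAP 4.6 subgroup text mentions only the adjusted means and their CIs, so the shell already goes further than the text. No p-values are planned, and the results go to the statistical appendix. The display list in SAP Attachment 1 is an embedded file and cannot be read here.

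**The concern.** Choosing a fit range for future studies raises two questions. The first is how large and how variable the adhesive effect is in each group, and the planned fits answer it. The second is whether the effect differs between groups, and no planned row estimates that.

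The risk lies in interpretation. Without a printed contrast, it is natural to note which group's CI excludes zero and conclude that the method works in one group and not in the other. That reading can produce an apparent difference where there is none. The opposite habit, checking whether the two CIs overlap, can miss a real difference. Either could influence the inclusion criteria of the next study. The primary endpoint is not affected.

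**Working it through.** The readable text gives no variance, effect size or power for the subgroups, so there is no planned figure to reproduce. All effect sizes below are assumptions, in units of the SD of the within-subject difference (conventional minus no adhesive).

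**Inputs.** About 48 subjects and a 50±10% split (Protocol 10.1), so 24/24, with 20/28 as an uneven case. 95% CIs (SAP 4.6). Complete data assumed.

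**Reading 1: exactly one CI excludes zero, with the same true effect in both groups.** Let p be the noncentral-t probability that a paired 95% CI with n = 24 (23 df) excludes zero. The groups are independent, so the probability of discordance is 2p(1−p).

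| True effect | p | 2p(1−p) |
|---|---|---|
| 0.3 | 0.291 | 41% |
| 0.4 | 0.467 | 50% |
| 0.5 | 0.650 | 45% |
| 0.8 | 0.963 | 7% |
| 1.0 | 0.997 | 0.6% |

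At 20/28 the first three become 42%, 51% and 47%. With the crossover model's 2n−4 = 44 residual df in place of 23, they are 42%, 50% and 44%.

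**Reading 2: the CIs do not overlap.** This compares it with a direct CI for the contrast, using 400,000 simulated pairs of independent fits (24/24, 44 df each, Satterthwaite df for the contrast).

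| True low-high difference | CIs do not overlap | Direct CI excludes zero |
|---|---|---|
| 0 | 0.6% | 5.0% |
| 0.5 | 14% | 40% |
| 0.8 | 48% | 78% |
| 1.0 | 73% | 93% |

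**Precision of the proposed row.** SE = sqrt(1/n_low + 1/n_high).
- 24/24: sqrt(1/24 + 1/24) = 0.289; t with 88 df is 1.987; half-width 0.574.
- 20/28: SE 0.293; half-width 0.582.
- 22/22 (assumed dropout of about 8%): SE 0.302; half-width 0.600.

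An 80% chance that the CI excludes zero needs a true difference of 0.82 at 24/24.

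**Rounding in the shell.** Differences are printed to 0.01 g, so each may be off by up to 0.005 g and a hand-computed contrast by up to 0.01 g (10 mg). The protocol introduction quotes earlier masses of 51 and 35 mg for maxillary dentures, which are 51 − 35 = 16 mg apart, and no more than 20 mg combined in another study. If masses here are similar, rounding could swamp the contrast. Protocol 7.2.1 has masses weighed to four decimals, so the precision exists in the data. Masses may also be larger here, because screening requires visible migration under each denture.

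**The case against.** The strongest reply is that nothing is defective. The objective and endpoint are within group, Tables 14.2.5 and 16.1.9.3.1 deliver them, and the two documents agree on the plan. That stands. A reader might infer that the SAP fails its subgroup objective or departs from the protocol; neither is so.

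A reader might also infer that, as planned, only two CIs can be set side by side. The shell does not support that. It prints each group's difference with its SE, and the groups contain different subjects, so the contrast is a subtraction with SE sqrt(SE_low² + SE_high²). What remains is narrower: the contrast is not pre-specified or reported, and printed rounding may spoil it. A new row in the same two-decimal format would share that weakness, so the fix must ask for more decimals.

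The misreadings above are not rules in the plan, which has no success criterion and reports no p-values. That stands too; they are risks of informal reading.

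Inclusion criteria depend on more than the contrast. Each group's effect relative to its variability matters, and a difference in grams depends on scale. Take an assumed 40% reduction in both groups, from 0.10 g and 0.05 g without adhesive. The effects are −0.04 and −0.02 g, so the contrast is non-zero although the proportional effect is identical. This is why the separate fits should stay and the scale should be stated.

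Finally, the contrast is imprecise. That is true, and a printed CI shows how imprecise.

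**Conclusion.** This is an optional improvement to exploratory reporting, not an error. The planned output answers the objective as worded but leaves one part of the stated purpose, whether the adhesive effect differs by denture fit, without a reported estimate. If readers judge by which CI excludes zero, a false impression of a difference would arise in about 41-50% of trials at assumed common effects of 0.3-0.5 SD, but in only 7% at 0.8 SD and 0.6% at 1.0 SD. The size therefore depends on an effect that the documents do not give. The other assumptions are about 24 subjects per group, normal differences and complete data.

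The row would inform the inclusion criteria without settling them. It tests only the 6-14 / 15-18 cut, and its half-width is about 0.57 SD.

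**What to change.** Keep the separate subgroup fits. Add one sentence to SAP 4.6 and one row to Table 16.1.9.3.1:

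- **Contrast:** (conventional minus no adhesive) in the low group minus the same in the high group, with SE and 95% CI and no p-value.
- **Computation:** from unrounded results of the two independent fits, SE = sqrt(SE_low² + SE_high²) with Satterthwaite df, or from an equivalent joint model.
- **Display:** enough decimals for masses of tens of milligrams.
- **Scale:** state that the contrast is on the scale of the fitted model, that is grams, or the transformed scale if SAP 4.6's transformation option is used.
- **Interpretation:** state that with about 24 per group a CI spanning zero does not show that denture fit is irrelevant.

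Do not extend this to a between-group Hodges-Lehmann shift under the rank-based fallback. In a simulation with assumed lognormal differences (sigma 1, 24/24, equal mean effects), its 95% CI covered the true zero mean contrast only about 77% and 62% of the time at SD ratios of 1.5 and 2.

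The cost is two or three sentences of SAP text and one table row, with no new data, subjects or visits.

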4.7 Analysis of Safety

Safety analysis will be performed on all subjects in safety population, unless specified otherwise.

4.7.1 Adverse Events and Serious Adverse Events

Adverse events (AE) recorded during the study will be mapped to a system organ class (SOC) and preferred term (PT) using the current medical dictionary for regulatory activities (MedDRA).

Prior to database lock all AEs will be reviewed by the Clinical Research Director (or designee) and categorized as either oral or non-oral.

Treatment emergent adverse events (TEAEs) are defined as new AEs that occur on or after the date/time of the first supervised use of the randomized treatment (dentures were inserted). Events with an onset date/time prior to first use of a treatment (in period 1) will be considered as non-treatment emergent.

In this crossover trial, events will be assigned to the treatment group based on the treatment being received at the onset of the event. TEAEs with an onset date time between treatments visits will be assigned the treatment received in the previous period. TEAEs with an onset after last treatment or the end of the study will be assigned to the treatment taken in the last period. If an emergent AE continues to another treatment period, the AE will be considered emergent in the period in which it started.

The following summary tables and listings will be presented by treatment group:

- Table of TEAEs by oral/non-oral and PT (Table 14.3.1.1.2)
- Table of TEAEs by SOC and PT (Table 14.3.1.1.1)
- Table of TEAEs related to study treatment by oral/non-oral and PT (Table 14.3.1.2)
- Listing of all AEs (including all subjects: Listing 16.2.7.1.1 for all randomized subjects; Listing 16.2.7.1.2 for non-randomized subjects)
- Listing of death (Listing 14.3.2.1)
- Listing of non-fatal serious AEs (Listing 14.3.2.2)
- Listing of TEAEs leading to withdrawal (Listing 14.3.2.3)
- Listing of TEAEs classified as oral (Listing 14.3.2.4)

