a There will be a 60±5 minute wait after dentures are inserted and the commencement of the food occlusion testing.

b At visits 2-4 the OST examination will be performed before product application and also after the denture removal and peanut recovery.

c Dentures will be cleaned both prior to and after the food migratory adequacy (V1) or food occlusion testing assessment (V2-4).

d Pregnancy testing at Visits 3 and 4 are only required should more than 30 days have elapsed between the treatment visit and the previous pregnancy test.

e For females of childbearing potential per [Section 7.3.2](#).

Document Name	208397 Clinical Protocol 2.docx	Document Identifier	Effective Date
Type	Version		
eldo_controlled	2.0; Most Recent; Effective; CURRENT	090032d580db1b91	24-Oct-2017 08:49:05

Sodium-calcium mixed partial salt of poly(methylvinylether/maleic acid) and carboxymethylcellulose

208397

Final Clinical Protocol, 20 Oct 2017

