8 ADVERSE EVENT AND OTHER EVENTS OF SPECIAL INTEREST REPORTING

8.1 Definitions of Adverse Events and Serious Adverse Events

8.1.1 Adverse Event

An AE is any untoward medical occurrence in a clinical study participant, temporally associated with the use of an investigational or washout product or medical device, whether or not considered related to the investigational or washout product or medical device.

NOTE: An AE can therefore be any unfavourable and unintended sign (including an abnormal laboratory finding), symptom, or disease (new or exacerbated) temporally associated with the use of a study treatment.

Events Meeting the AE Definition:

- Any abnormal safety assessments (e.g., OST findings, including those that worsen from baseline, considered clinically significant in the medical and scientific judgment of the investigator (ie, not related to progression of underlying disease)).
- Exacerbation of a chronic or intermittent pre-existing condition including either an increase in frequency and/or intensity of the condition.
- New conditions detected or diagnosed after study treatment administration even though it may have been present before the start of the study.
- Signs, symptoms, or the clinical sequelae of a suspected drug-drug interaction.
- Signs, symptoms, or the clinical sequelae of a suspected overdose of either study treatment or a concomitant medication. Overdose *per se* will not be reported as an AE/SAE unless it is an intentional overdose taken with possible suicidal/self-harming intent. Such overdoses should be reported regardless of sequelae.
- "Lack of efficacy" or "failure of expected pharmacological action" *per se* will not be reported as an AE or SAE. Such instances will be captured in the efficacy assessments. However, the signs, symptoms, and/or clinical sequelae resulting from lack of efficacy will be reported as AE or SAE if they fulfil the definition of an AE or SAE.

Events NOT meeting the AE definition:

GlaxoSmithKline Consumer Healthcare Confidential

Template Version Effective: 22-Jun-2017

Page 36 of 62

Document Name	208397 Clinical Protocol 2.docx	Document Identifier	Effective Date
Type	Version		
eldo_controlled	2.0; Most Recent; Effective; CURRENT	090032d580db1b91	24-Oct-2017 08:49:05

Sodium-calcium mixed partial salt of poly(methylvinylether/maleic acid) and carboxymethylcellulose

208397

Final Clinical Protocol, 20 Oct 2017

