8.7 Follow-up of Adverse Events and Serious Adverse Events

After the initial report, the investigator is required to proactively follow up with each subject and provide further information on the subject's condition.

All AEs/SAEs will be followed until resolution, until the condition stabilises, until the event is otherwise explained, or until the subject is lost to follow-up.

The investigator is obligated to perform or arrange for the conduct of supplemental measurements and/or evaluations as may be indicated or as requested by GSK to elucidate as fully as possible the nature and/or causality of the AE or SAE. This may include additional laboratory tests or investigations, histopathological examinations, or consultation with other health care professionals.

New or updated information will be recorded in the originally completed CRF.

The investigator will submit any updated SAE data to GSK within 24 hours of receipt of the information.

Investigators are not obliged to actively seek AEs or SAEs in former subjects. However, if the investigator learns of any SAE, including the death, at any time after a subject has been discharged from the study, and considers the event reasonably related to the investigational product or study participation, the investigator will promptly notify GSK by emailing the information to the GSK CH Clinical Operations Safety Reporting email box PPD. The GSK CH Study Manager or designee will be responsible for forwarding the information to the Case Management Group, Global Clinical Safety and Pharmacovigilance group mailbox at GSK PPD.

The investigator will submit any updated SAE data to GSK within the designated reporting time frames.

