10.2.6 Safety Analysis

All AEs will be coded using MedDRA. AEs will be categorised as oral and non-oral by the Clinical Research Director/ Scientist or designee prior to database lock. Treatment-emergent adverse event (Oral AEs as well as all AEs) will be associated with the most recent treatment received. The number of AEs and number of subjects with AEs will be listed and tabulated by treatment. The results of OST exams will be listed. Incidents will be listed.

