3.1 Baseline Definition

A baseline definition is not required for this trial as no baseline measurements are performed or required for the summaries and analysis.

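### The SAP has no rule for an adverse event that worsens after a later treatment, so the worsening may go uncounted under that treatment

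*SAP*

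**What the plan says.** **Counting and assignment (SAP 4.7.1).** The definition is limited to new events: "Treatment emergent adverse events (TEAEs) are defined as new AEs that occur on or after the date/time of the first supervised use". In this crossover, "events will be assigned to the treatment group based on the treatment being received at the onset of the event". Events starting between visits go to the preceding treatment. For events that persist, "If an emergent AE continues to another treatment period, the AE will be considered emergent in the period in which it started". Nothing is said about an increase in severity.

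**Assignment in the protocol (10.2.6).** Treatment-emergent events "will be associated with the most recent treatment received". This fits assignment by onset and is equally silent on worsening.

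**What counts as an adverse event (protocol 8.1.1).** The note to the definition covers exacerbated as well as new signs, symptoms and disease. The list of qualifying events includes this item: "Any abnormal safety assessments (e.g., OST findings, including those that worsen from baseline", subject to the investigator judging the finding clinically significant. A further item covers exacerbation of a chronic or intermittent pre-existing condition.

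**How follow-up is recorded (protocol 8.7).** "New or updated information will be recorded in the originally completed CRF".

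**When worsening could be seen (protocol Table 1-1, footnote b).** "At visits 2-4 the OST examination will be performed before product application and also after the denture removal and peanut recovery".

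**Outputs.** SAP 4.7.1 presents all and related treatment-emergent events, non-fatal serious events and withdrawals by treatment group. The table templates have no severity breakdown. The template for Listing 16.2.7.1.1 gives one period, one start date and one intensity per event. OST results are listed only (SAP 4.7.2).

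**The concern.** Tolerability of the adhesive is the only safety objective, and treatment-emergent adverse events are its only endpoint (protocol Table 2-1). The by-treatment tables are where a reader will look for it.

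Take a subject with mild irritation after the no-adhesive visit, still present at the next visit, which becomes moderate after adhesive. If the site updates the existing record, onset does not change and the event is one count under No Adhesive. The adhesive column shows nothing. If the site opens a second record, the worsening has its own onset and is counted under adhesive. The same clinical course gives different tables according to site habit.

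The related-event table and the withdrawal listing are exposed in the same way. If the event is updated to related, or leads to withdrawal, only after adhesive, assignment by onset still shows it under No Adhesive.

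**Working it through.** The plan states no figure on this point, so there is none to reproduce. The check has two parts: how the rules act together, and the scale on which they could act.

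**1. Two ways of recording the same course**

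The event starts after treatment X, is ongoing at the next visit, and worsens after treatment Y.

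| Step | Worsening entered as a new record | Worsening entered as an update |
|---|---|---|
| Support in the protocol | 8.1.1 (exacerbated signs; worsened OST findings) | 8.7 (updates go on the original record) |
| Onset held in the data | Original onset, plus the date of worsening | Original onset only |
| SAP 4.7.1 assignment | Original to X, worsening to Y | X only |
| Count under X | 1 | 1 |
| Count under Y | 1 | 0 |

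The count under X is the same in both columns. The count under Y is what changes.

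The exacerbation item in 8.1.1 does not clearly settle which route applies. It concerns pre-existing conditions, and the list of non-qualifying events in the same section uses that term for conditions present or detected at the start of the study. No section tells sites to open a new record when an event that arose on study gets worse.

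**2. Scale**

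Inputs: about 48 subjects, maximum 50 (protocol section 3); three periods; six sequences (SAP Appendix 1). Assumptions: 8 subjects per sequence and no dropout. Equal allocation is not stated in the documents.

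- Treatment periods: 48 × 3 = 144.
- Transitions to a further treatment: 48 × 2 = 96. The gap can act only here.
- Each ordered pair of treatments is adjacent in two of the six sequences: 2 × 8 = 16 transitions per pair.
- No adhesive to adhesive (two pairs): 2 × 16 = 32. Adhesive to no adhesive: 32. Between the two application patterns: 32. Sum: 96.
- One subject in a treatment column: 1/48 = 2.1 percentage points (1/50 = 2.0).

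No rate of worsening is given. The rates below are assumed, to show scale only.

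| Assumed share of transitions with a worsening event | All 96 transitions | The 32 from no adhesive to adhesive |
|---|---|---|
| 1% | 96 × 0.01 = 1.0 | 32 × 0.01 = 0.3 |
| 2% | 96 × 0.02 = 1.9 | 32 × 0.02 = 0.6 |
| 5% | 96 × 0.05 = 4.8 | 32 × 0.05 = 1.6 |

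The last column matters most for the safety objective, because only those transitions can hide a worsening on adhesive behind a no-adhesive onset. Transitions between the two patterns affect the comparison of patterns, but the event stays within the same adhesive.

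**The case against.** **Assignment by onset is correct.** The SAP sentence is about continuation, and an event belongs with the treatment under which it began. This stands. A reader might infer that events are assigned to the wrong treatment and that the earlier column's event count is inflated. The documents do not support that: the original event stays where it is under any sensible rule, and only the later worsening can go uncounted.

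**The protocol already allows a new record.** This stands in part. Section 8.1.1 lets a site record an exacerbation as an event, and section 8.7 does not forbid it. It is therefore too much to say that the rules always charge the whole course to the earlier treatment. But permission without an instruction leaves the count to the site.

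**Carry-over should be uncommon.** Protocol 1.2.1 considers 2-30 days adequate rest for the oral soft tissues, and an OST examination and eligibility check precede each application. This stands against any claim that worsening across periods is the expected pattern. The check does not exclude every mild finding: exclusion criterion 14 turns on whether, in the investigator's opinion, the finding would interfere with the conduct of the study.

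**The SAP's position on baseline is not a contradiction.** SAP 3.1 states: "A baseline definition is not required for this trial as no baseline measurements are performed or required for the summaries and analysis". A reader might set this against the worsening clause in protocol 8.1.1. However, OST data are only listed, so the analysis needs no baseline, and worsening is the investigator's clinical judgement. The objection stands in full.

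**The listings show it anyway.** Listing 16.2.7.3 gives OST results before and after treatment at each visit. This helps, but protocol 7.3.1 records normal or abnormal with a location and brief description, so a worsened finding may read as abnormal both times. The adverse event listing has one intensity per event.

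**Little depends on it.** The tables are descriptive, there is no success criterion, and protocol 11.3 says the study is not intended to assess safety and efficacy. This limits the weight of the point without removing it.

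**Conclusion.** There is a minor gap worth closing. Neither document says how to count an adverse event that worsens after a later treatment, and protocol 8.1.1 and 8.7 support different ways of recording it. A worsening after adhesive may be missing from the adhesive column, and a change to related or to withdrawal may be shown under the earlier treatment.

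The number affected cannot be estimated from the documents and is probably small. A reader might multiply assumed rates, say 5-10% of transitions with an ongoing oral event and 20-40% of those worsening, to get 96 × 0.05 × 0.20 = 1.0 up to 96 × 0.10 × 0.40 = 3.8 events, and set that beside the count in one column. Those rates appear nowhere in the documents, the total spans every direction of transition, and with balanced sequences only a third (32 of 96) run from no adhesive to adhesive. What can be said is that each affected subject is worth 2.1 percentage points of a 48-subject column.

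This rests on reading 8.7 as allowing an update in place of a new record. That is a natural reading, but the text does not require it.

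**What to change.** 1. **SAP 4.7.1.** Add: *An adverse event that increases in severity after a later treatment is counted as a treatment-emergent event of the treatment received at the time of worsening; the original event remains in the period in which it started.*
2. **Recording instruction.** Tell sites to enter such a worsening as a new adverse event with its own onset date, and reconcile protocol 8.1.1 and 8.7 accordingly. The severity categories in protocol 8.4.1 can define the increase.
3. **Reference for OST findings.** Name the existing pre-application examination at each visit as the reference for judging worsening. No new assessment is needed, and SAP 3.1 needs no amendment for the analysis.

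The cost is one SAP sentence, one completion instruction and a few more adverse event records. One clinical course may then be counted in two treatment columns, so a table footnote should say so. In the Overall column the subject is still counted once, while the number of events rises. The rule should be settled before database lock.
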